## 8.7.1.2. ICC (NL)

If data are missing, patients are calculated as nonresponders. However, since there is prospective follow-up and centers are alerted if a visit is in the near future, missing data is limited. ICC does not use imputation for missing values.

#### 8.7.1.3. SWIBREG (SWE)

Missing baseline values are expected to be rare. For this reason, imputation for missing data points will not be performed in this study. However, variables with missing data will be described.

## 8.8. Quality Control

## 8.8.1. ENEIDA (ES)

During the preparation of the analytic file for this study, quality control measures will include checks for legitimate values for each categorical variable and logic checks for dates. There are no plans to systematically clean the ENEIDA data via queries after data are received.

The chart abstraction data will be checked for content by edit checks programmed into the PDF form, as stated in the edit check specifications document that will be prepared. In addition, sites will be queried for nonsensical data (e.g. dates that appear to be in the wrong format).
#### 8.8.2. ICC (NL)

Data are filled in at the participating center by the treating physician or nurse. The ICC fellow regularly visits the participating centers and checks the data at random or in more detail if necessary. There are quality checks build in the eCRF (e.g. a maximum amount of digits for CRP). After receiving the SPSS file by MEMIC, data is checked for legitimate values for each variable and logic checks for dates.

#### 8.8.3. SWIBREG (SWE)

This study uses data existing within SWIBREG and several national registers in Sweden including NPR and PDR. Data management will include cleaning of data to remove illogical values, derive study variables, and structure the data to perform the required statistical analyses. All data management will be conducted on servers at KI using standard statistical software including SAS, STATA, and R.

The quality control of data and statistical programs developed will include:

- Adherence to requirements and specifications outlined in the SAP. Any deviations will be reported
- Review of individual data linkage across registers
- Review of log files (errors, outliers, warnings, missing values, and notes)
- Review of distributions (histogram, min-max, median, percentiles, mean, standard deviation) of continuous variables and frequencies for all possible values of discrete variables

Quality control of specific reports is made in accordance with standard operating procedures through internal review by at least 2 staff members: a statistician/epidemiologist responsible for assessing technical aspects and integrity of the results, and a clinical expert responsible for assessing the plausibility and consistency of observed rates and risks in relation to what is previously known on the topic. Any results that are marked as questionable or inconsistent are reanalyzed/verified or rephrased until no more issues are identified.

### 8.9. Limitations of the Research Methods

This non-interventional, registry-based DUS aims to evaluate the effectiveness of the aRMMs for filgotinib prescribed for treatment of patients with UC using information collected by 3 European IBD registries. Despite the strengths of this DUS, results must be evaluated considering their limitations.

Most importantly, as per the updated filgotinib SmPC, it is recommended that e.g. in patients 65 years of age or older, or those with history of atherosclerotic CVD disease or other CV risk factors, or in patients with malignancy risk factors, filgotinib should only be used 'if no suitable treatment alternatives are available'. Whether suitable treatment alternatives are available for a patient is an individual assessment made by the HCP together with the patient, taking into account patient characteristics and preferences. Given the nature of these assessments, a non-interventional study with secondary data use will not be able to reliably assess whether 'no suitable treatment alternatives' were available. This limitation is partly addressed, however, by

assessing the previous history of UC treatment prior to initiation of filgotinib and additional information such as reasons for switching prior UC treatment(s).

The quality of the registry data is not comparable to that of clinical trials due to less stringent data quality monitoring. The accuracy of the data depends mainly on the professional who records the data and the patient's responses. This is important given that the DUS examines medical history which may not be available in the clinical records and thus relies on memory. In addition, there may be heterogeneity in data quality within centers, and between countries. This could inflate (but also mask) genuine differences between the results from the registries.

Furthermore, not all information that is relevant in the context of this DUS may be captured by all registries. For instance, in the context of skin malignancies (NMSC), none of the registries systemically records information on periodic skin examination. Therefore, this cannot be reliably followed or measured in any of the three registries used in this DUS. Moreover, not all registries capture the same information, nor is the process of data capturing the same. While e.g. in SWIBREG – due to data linkage to various other Swedish data sources and registries – the vast majority of variables will be available, in ENEIDA information on many variables will need to be extracted from EMRs.

The analyses of this DUS will be restricted to the period after the EC decision date on the JAKi Article 20 procedure (10 March 2023), and therefore not include filgotinib data of the pre-referral period. The rationale for this is that the number of patients identified in the registries exposed to filgotinib in the pre-referral period, i.e. between the filgotinib EU approval date (Netherlands: 12-Nov-2021; Spain: 01-May-2023 [= date of reimbursement approval of filgotinib in Spain on a national level]; Sweden: 12-Nov-2021) and the EC decision date is very limited (ICC: n=54; ENEIDA: n=19; SWIBREG n=44).

Any non-interventional study can suffer from bias, specifically, selection or information bias. However, this study aims to capture up to 500 consecutive patients per registry initiating filgotinib in the observational period. Therefore, this study will reflect the clinical practice and characteristics of these patients.

### 8.10. Other Aspects

#### 8.10.1. Sponsor's and Investigator's Responsibilities

The MAH reserves the right to fully terminate this non-interventional PASS at any time ("Full Termination"), while each registry (i.e. ENEIDA, ICC, and SWIBREG) may terminate its own participation in this PASS according to the contractual terms and conditions applicable to each collaboration ("Partial Termination"). Should either a Full Termination or a Partial Termination be necessary, the relevant parties (i.e. the MAH, each registry and other participating parties) will collaborate to arrange discontinuation procedures and notify the appropriate regulatory agencies, where applicable. For studies conducted for a commitment to a regulatory authority, any consideration for termination of the study will be discussed with the applicable authority beforehand.

The name and address of each third-party vendor (e.g. scientific service provider [e.g. RTI-HS]) used in this study and the sponsor's study team members will be maintained in the investigator's and sponsor's files as appropriate.

Prior to study start, this protocol together with all relevant documentation needs to be submitted to the respective regulatory authorities and IEC/IRBs for review and approval in compliance with current regulations before the study can start.

## 9. **PROTECTION OF HUMAN SUBJECTS**

#### 9.1. Good Pharmacoepidemiology and Pharmacovigilance Practices

The study will be conducted in accordance with the EMA – Guideline on GVP Module VIII – Post-Authorization Safety Studies, including archiving of essential documents.

# 9.2. Institutional Review Board or Independent Ethics Committee Review

#### 9.2.1. ENEIDA (ES)

The study protocol will be reviewed and endorsed by GETECCU (the scientific society maintaining the ENEIDA registry) and the study's reference ethics committee (to be determined), In addition, the ethics committee of each hospital participating in the chart review component of the study will also review and approve the protocol, commensurate with local law. The study will be registered in the Spanish Registry for Clinical Studies.

#### 9.2.2. ICC (NL)

The registry study protocol was reviewed and approved by the ICC (the scientific society Initiative on Crohn and Colitis), Commissie Mensgebonden Onderzoek (CMO) Radboudumc and ethics committees of the participating centers.

#### 9.2.3. SWIBREG (SWE)

This study will make secondary use of existing data collected by SWIBREG and other national Swedish registers. The data are at individual level, pseudonymized, and stored on secure servers at KI. The SWIBREG register linkage database does not contain any identifying information from patients (for example, name), except for a unique number assigned for the purpose of linking files. This comparative safety study has been approved by the Regional Ethical Review Board in Stockholm (2022-01-14/2021-06209-01). A renewed ethical approval will be sought as needed for the duration of the study.

# 9.3. Informed Consent

### 9.3.1. ENEIDA (ES)

This non-interventional study will involve no administration of any therapeutic agent according to the study protocol; patients in ENEIDA are treated in the setting of usual clinical care. Patients whose data are included in ENEIDA previously consented to have their health information included in this database.

For the current study, some of the variables of interest extend beyond the field of UC and are not routinely collected in ENEIDA. As a consequence, a new IC will need to be obtained for this PASS for all patients that participate in the chart abstraction component of the study. If necessary, because of low enrolment in the chart abstraction component, patients for whom an IC cannot be obtained may still participate in the study addressing only those objectives that can be assessed using data collected in the registry.

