## 8. **RESEARCH METHODS**

## 8.1. Study Design

This DUS is based on a non-interventional, post-authorization, prospective, multicountry, registry-based, longitudinal follow-up (cohort) design with secondary use of data collected from 3 European IBD registries. The registries to be used are: (i) the ENEIDA Register from Spain (ES), (ii) the ICC Register from the Netherlands (NL), and (iii) SWIBREG from Sweden (SWE). Data from the 3 European IBD registries may be enriched with additional (secondary) data collection information if needed and applicable. The study fulfills the criteria of a non-interventional PASS (category 3) in accordance with the commitment to the EMA and to the MHRA from the United Kingdom.

The study population will include up to 500 consecutive adult patients of any sex with UC and initiating treatment with filgotinib following implementation of the aRMMs after EC's final decision on Article 20 (decision date: 10 March 2023) per registry.

The observational period will be 4 years starting after the EC decision date on Article 20 (i.e. after 10 March 2023). It will include all follow-up time until dropout for the included patients.

Two reports will be generated: an interim report with 2 years of data collection (to be submitted within 9 months after end of interim data collection), and a final study report with 4 years of data collection (to be submitted within 12 months after end of data collection).

*Note*: The end of data collection, i.e. the timepoint by which the analytical dataset to perform the statistical analyses is completely available, is highly correlated with the process of chart abstraction (ENEIDA) or data linkage (SWIBREG). Thus, interim and final study reports will not be available within 9 and 12 months, respectively from the end of the observational periods.

In addition, in the ENEIDA registry, the set-up of ethics approvals, contracts and necessary activities (e.g. trainings) with all individual centers before chart abstraction can begin will likely take up to 2 years, based on prior experience in conducting similar PASS in this registry. It is important to keep this in mind for the scope of the interim report since it will be limited to information readily available in the ENEIDA registry (i.e. without supplementing its information with chart abstraction).

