#### 8.4.1.3. Study Complementary Data Source: Medical Chart Abstraction

The information collected in the ENEIDA registry can be supplemented by the participation of clinical investigators at individual sites in studies where additional information is collected via electronic questionnaires. These questionnaires may collect information on variables that are not recorded in the ENEIDA registry or for which a large number of missing values is expected. Questionnaires can also be used to validate study endpoints and exposure to the drugs of interest that are identified in the ENEIDA automated registry via comparison with patient EMRs.

For the present study, a specific informed consent (IC) of patients will be required to access their EMRs (see also Section 9.3.1) since most of the questions of interest of this PASS fall outside the scope of the information collected by ENEIDA.

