# Figure 2 Estimated 95% Confidence Interval by Study Size and Underlying Proportion (Assuming a Binomial Distribution)

## 8.6. Data Management

## 8.6.1. ENEIDA (ES)

This study will involve analysis of secondary data from the ENEIDA registry, as described in Section 8.4. The automated data are maintained and managed by the ENEIDA registry in a password-protected MySQL database, which is maintained on a server in a secure facility. The investigator or qualified designee is responsible for verifying the accuracy of patient data as it is entered into the ENEIDA registry. All analyses will be conducted using SAS software.

This study involves chart review for all patients exposed to filgotinib identified in the automated data. Linkage between the automated record and the patient record will be based on the patient identification number and clinical site identifier.

Data will be accessed by Research Triangle Institute Health Solutions (RTI-HS) according to ENEIDA's standard practice. RTI-HS will log on to the ENEIDA secure server, download the data files, and store the data in a secure server in Barcelona with backups in the EU. Only selected RTI-HS personnel in Barcelona will have access to the data. Once the data are received,

RTI-HS will develop a data dictionary using SAS PROC CONTENTS. The data dictionary will document any data transformations applied to the received data sets to create the analytical datasets. The data dictionary will include variable names, formats, and any SAS code used to create derived variables from raw variables.

The transfers of data from ENEIDA may include data for patients who do not qualify for the analytic purposes of the present study. However, these data may be used to determine whether the analytic database is representative of the ENEIDA registry data in its totality. All data received from the registry will be covered by the IC signed by all patients at enrolment in ENEIDA. Chart abstraction will require patients to sign a study-specific IC to be able to obtain information of variables that are not part of the ENEIDA registry scope (see also Section 9.3.1). Data not used for the analysis will be filtered out at RTI-HS. Only data essential to the planned analyses will be retained in the analytic database.

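### Section 9.3.1 keeps ENEIDA patients without study-specific consent only if chart enrolment is low, which conflicts with registry-consent eligibility and with the consecutive-inclusion claim

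*Protocol*

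**What the plan says.** Four parts of the protocol decide which Spanish patients are analysed.

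- **Section 9.3.1 (consent, ENEIDA).** The study-specific consent is a condition for chart work: "a new IC will need to be obtained for this PASS for all patients that participate in the chart abstraction component of the study". For patients without it: "If necessary, because of low enrolment in the chart abstraction component, patients for whom an IC cannot be obtained may still participate", and then "addressing only those objectives that can be assessed using data collected in the registry".
- **Section 8.2.2 (inclusion).** The only consent named is the one the registry itself requires. Neither prior history nor a minimum length of follow-up is demanded. Section 8.2.3 does not make lack of study-specific consent an exclusion.
- **Section 8.6.1 (data management, ENEIDA).** "All data received from the registry will be covered by the IC signed by all patients at enrolment in ENEIDA". The same section states "This study involves chart review for all patients exposed to filgotinib identified in the automated data", and later adds that abstraction requires the study-specific consent.
- **Section 8.9 (limitations).** Selection bias is answered by pointing to consecutive inclusion of up to 500 initiators per registry.

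Two further statements set the context. On timing, Section 8.1 says that ethics approvals, contracts and training "before chart abstraction can begin will likely take up to 2 years, based on prior experience in conducting similar PASS in this registry". On dependence, Section 8.4.1.3 says that "most of the questions of interest of this PASS fall outside the scope of the information collected by ENEIDA".

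**The concern.** Section 9.3.1 makes keeping a patient without the new consent an exception. The trigger is the number of patients enrolled for charts, not any sign that those missing differ from those present. If most patients consent, enrolment may look adequate and the remainder can be dropped, although nothing shows that they resemble the rest.

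The loss is avoidable for part of the study. Annex 3, Table 5 lists age, sex, prior advanced therapy, reasons for switching, and discontinuation with its date as available in ENEIDA. Dose, tuberculosis, serious infection and VTE are listed as available at least in part. These items feed the adherence objectives in Section 7 and need no new consent.

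Timing makes selection plausible. Index dates start after 10 March 2023, and abstraction may begin up to 2 years later. A patient who has died or been lost by then is among the hardest to ask. Death and loss also end follow-up under Section 8.2.4, so such patients would tend to have shorter observed treatment.

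There is also a risk between reports. The ENEIDA interim report uses registry data alone (Section 8.1). If the final report dropped patients without the new consent, the same registry measure would refer to a different population in each report.

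**Working it through.** **Step 1. Side-by-side reading.** Take an ENEIDA patient who starts filgotinib after 10 March 2023, has registry consent, and cannot give the study-specific consent.

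- Section 8.2.2: eligible.
- Section 8.6.1: registry data usable.
- Section 8.9: counted, since inclusion is consecutive.
- Section 9.3.1: kept only if chart enrolment is low, and then only optionally.

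The first three cannot all stand with the fourth. The protocol does not settle whether this patient is in the study.

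**Step 2. The protocol's own precision figures (Section 8.5).** With p = 10% and n = 300, SE = √(0.10 × 0.90 / 300) = 1.73%, and 10% ± 1.96 × 1.73% gives 6.6% to 13.4%. This matches the text. The rule of 3 gives 3/0.01 = 300, with exact detection 1 − 0.99^300 = 95.1%. No stated figure is in dispute.

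**Step 3. Is it a matter of numbers?** Take 500 initiators, the protocol's ceiling per registry. If 10% to 40% lack consent, 450 to 300 remain. Detection of a 1% contraindication goes from 1 − 0.99^450 = 98.9% to 1 − 0.99^300 = 95.1%. Loss of precision is minor.

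**Step 4. Is it a matter of selection?** Let p be the prevalence in all initiators, m the share without study-specific consent, and R the prevalence in that share divided by the prevalence p_c in consenters. Then p = (1 − m)p_c + mRp_c, so p_c = p / (1 − m + mR). Neither m nor R is in the protocol; the values below are assumptions. With p = 10% and 500 initiators:

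| m | n kept | R | p_c | Bias (points) | SE (points) |
|---|---|---|---|---|---|
| 10% | 450 | 2 | 10/1.1 = 9.1% | −0.9 | 1.4 |
| 20% | 400 | 1 | 10/1.0 = 10.0% | 0 | 1.5 |
| 20% | 400 | 2 | 10/1.2 = 8.3% | −1.7 | 1.4 |
| 20% | 400 | 0.5 | 10/0.9 = 11.1% | +1.1 | 1.6 |
| 30% | 350 | 2 | 10/1.3 = 7.7% | −2.3 | 1.4 |
| 40% | 300 | 3 | 10/1.8 = 5.6% | −4.4 | 1.3 |

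With R = 1 there is no bias. With R = 2 the bias passes one standard error once about 20% lack consent. With R below 1 the sign reverses. Fewer than 500 initiators would raise the SE but leave the bias unchanged.

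**Step 5. Direction.** If older patients were more often dead or lost before being asked, the share treated at 65 or over would look too small. For VTE, the objectives in Section 7 count stopping as compliance. Under-representing patients who stopped after a VTE would therefore make compliance look worse. There is no single direction.

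**The case against.** The strongest reply is that eligibility belongs to Section 8.2.2, which already includes these patients, so Section 9.3.1 is only loosely worded. This stands in part. A reader might infer from Section 9.3.1 that exclusion is the settled default for Spain. The protocol does not support that; it contradicts itself, and the contradiction is the finding.

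Other stronger readings also fail:

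- **Patients who stopped treatment are left out.** Stopping ends follow-up under Section 8.2.4, but the patient can remain in the registry and in care and can still be asked. Only death and loss are plausible groups. Even these are an inference, since the protocol does not say when consent is sought or how deceased patients are handled.
- **Results are biased towards good adherence.** Step 5 shows that the direction depends on the measure.
- **Discontinuation would be badly understated.** With 50% truly stopping and consent of 80% in continuers against 40% in discontinuers, observed discontinuation is 0.20/(0.20 + 0.40) = 33%; at 60% consent it is 0.30/(0.30 + 0.40) = 43%. The arithmetic is right, but nothing in the protocol supports these rates.
- **Section 8.6.1 promises chart review that consent forbids.** That section states the consent requirement itself, so this is an editorial matter.

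Two further points stand. The lag mainly affects early initiators in a 4-year period, and Section 8.9 dates Spanish reimbursement to 1 May 2023. Keeping patients without the new consent also cannot repair chart-dependent items: Table 5 lists atherosclerotic disease and BMI as not in the registry.

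Section 8.6.1 does allow transferred data to be used to check representativeness. That check is against the registry as a whole, and it does not say who is analysed.

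**Conclusion.** The concern holds as an internal conflict with a possible selection effect. Section 9.3.1 lets already-consented registry data be dropped on a trigger that reflects enrolment numbers, against Sections 8.2.2, 8.6.1 and 8.9. Patients who died or were lost before consent was sought may be left out, and this could bias registry-based measures as well as chart-based ones.

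The size is unknown. On the assumed values above it runs from zero to about 4 points on a true 10%, with either sign possible. That rests wholly on the share without consent and on how far they differ, and the protocol states neither. The point merits correction because the remedy is cheap. It does not show that the Spanish results will be biased.

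Who is in the study, and under which consent, is protocol content that hospital ethics committees review (Section 9.2.1). It should be settled there and not left to the SAP.

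**What to change.** 1. In Section 9.3.1, delete the low-enrolment condition. State that every eligible ENEIDA initiator is included for registry-available measures, and that study-specific consent decides only whether chart variables are added.
2. Report chart-based measures in consenters, with their own denominator. This matters because Section 8.7.1.1 mostly reads absent information as absence of the condition; mixing in patients without chart review would count unknowns as negatives.
3. Compare patients with and without study-specific consent on registry variables: age, sex, prior therapy, duration, discontinuation, and death or loss as far as the registry records them. The table layout can go in the SAP.
4. Reword Section 8.6.1 so that chart review covers exposed patients who have given the study-specific consent.

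The cost is a few sentences and one table, with no new data collection. The downside is that denominators will differ between registry-based and chart-based measures, and chart-only items will still describe consenters alone.
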